The greatest potential eventual implication of the proposed research is to improve the standard of care for a sizeable population in need of improved treatment approaches: young adults with SUD and emotional distress. If the adjunctive UP proves incrementally effective when added to TAU, it will contribute to evidence-based treatment guidelines for this underserved population. Effectively treating this group would reduce long-term disability and costs, improving overall functioning and reducing public health burden. By delivering adaptive strategies for emotional responding, this transdiagnostic group intervention offers a low cost, easily implemented treatment that may provide greater and more broad-based benefits than existing pharmacological and single-diagnosis therapies, and perhaps help prevent future SUD relapse. Eventual findings may be used to inform the development of guidelines for treatment of young adults (and potentially, other cohorts) with SUD and co-occurring emotional distress. This pilot study is the first, necessary step in obtaining preliminary data for future grant applications (e.g., K awards) to conduct a larger randomized trial adequately powered to examine short- and long-term efficacy, as well as intervention moderators (e.g., SUD type) and mediators.

II. SPECIFIC AIMS

We propose to conduct a pilot randomized controlled trial comparing a cognitive-behavioral, transdiagnostic, emotion-focused group intervention plus treatment as usual (UP + TAU) to TAU alone to within an existing comprehensive outpatient program for young adults with SUD and comorbid emotional distress (N=50). Participants will be randomized in a 2:1 ratio to UP + TAU or TAU alone conditions

Specific Aim 1: To evaluate the acceptability and feasibility of adding a transdiagnostic, emotion-focused group intervention (16 twice-weekly UP sessions) to TAU in a comprehensive outpatient program for young adults with SUDs and elevated emotional distress (N=50).

Hypothesis 1a. UP participants will report high satisfaction with and acceptability of the UP per Client Satisfaction Questionnaire (CSQ-8⁴⁷) and semi-structured clinical feedback interview.

Hypothesis 1b. UP participants will be less likely to drop out from treatment at the outpatient program during the study period than those in control condition.

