TAU condition: After randomization, participants randomized to the TAU condition will undergo usual care at ARMS for the next 8-10 weeks. Usual care at ARMS typically consists of a combination of up to 3 group therapy sessions per week, individual weekly therapy, and/or psychopharmacology appointments as needed. Some ARMS patients are offered and choose to engage in all three treatment modalities (group therapy, individual therapy, and psychopharmacology), whereas others only engage in one treatment modality. No requirements will be placed on TAU participants with regard to TAU dosage and TAU will be consistent with each participant's clinical treatment plan at ARMS; however, TAU attendance (e.g., number of appointments) for all participants will be tracked by study staff. Four to 6 weeks after randomization, TAU participants will complete a mid-treatment assessment, during which they will complete the same self-report questionnaires (plus TLFB and concomitant treatment log with a study clinician) administered at the screening/baseline visit (see *Measures*). Eight to 10 weeks after randomization, they will repeat the same measures for the in-person "post-treatment" assessment. During both the mid- and post-treatment assessments, should a participant report suicidal thoughts in the past week on the SITBI-SR or clinically significant increases in NSSI, a clinical risk assessment (including severity of ideation and presence of plan, intent, and access to means) will be conducted by a study clinician in order to ensure participant safety and that the

participant remains stable to be treated in an outpatient setting. After completing the post-treatment assessment, their study participation will be complete.

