UP + TAU condition: After randomization, participants randomized to the UP + TAU condition will undergo TAU at ARMS and be offered 16 additional, twice-weekly group UP sessions, also at ARMS (see *Intervention*). Participants in the UP + TAU condition will undergo the same midand post-treatment assessments as the TAU condition, plus the CSQ-8 and a semi-structured interview to collect feedback about the intervention (see *Measures*). The mid-treatment assessment will occur after each participant's 8th UP session OR between 4-6 weeks after randomization, and the post-treatment assessment will occur within two weeks after each participant's 16th UP session. The same risk assessment procedures for mid- and post-treatment assessments used in the TAU condition will also apply to the UP + TAU condition. Should a UP + TAU participant condition have two consecutive unplanned absences from a UP group session, up to three attempts to contact will be made regarding their absence. There will not be a maximum number of missed UP sessions warranting a participant to step out of the 16-session group protocol. After completing the post-treatment assessment, their participation in the study will be complete.

Group UP sessions will take place at the ARMS program at MGH. Study assessment visits (screening/baseline, mid-treatment, and post-treatment) may take place at the ARMS program, the Depression Clinical and Research Program (DCRP), or the Center for Addiction Medicine (CAM) at MGH. Study staff may walk participants between ARMS and the DCRP or CAM as needed.

In sum, the proposed study involves the following points of contact: (1) obtaining informed consent and screening/baseline assessment, (2) mid-treatment assessment involving self-report questionnaires and TLFB, (3) post-treatment assessment involving self-report questionnaires and TLFB (primary endpoint), and (4) 16 twice-weekly group UP sessions for those randomized to the UP + TAU condition.

If participants are unable to complete the clinician-rated measures in-person at their mid- or post-treatment assessments, they will be given the option to complete this portion of the visit via phone call with a study clinician. Should any risk issues arise, the clinician will complete a risk assessment while on the phone with the participant. A licensed clinician will always be on-site for consultation as needed during assessments conducted over the phone.

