Participants will make \$100 for completion of the three assessments (\$25 for the pre- and midtreatment assessments, and \$50 for the post-treatment assessment) and up to an additional \$80 for session attendance. Session attendance will be compensated as follows: participants will receive \$5 per session attended (up to 16 UP sessions in the UP+TAU group and up to 16 TAU sessions in the TAU along group). This amount represents approximate cost of travel to/from up to two sessions per week. In the TAU group, the number of possible sessions a patient can attend a week varies depending on the patient's individualized (clinical) treatment plan at ARMS; thus, receiving \$5 per session attended (for up to 2 weekly sessions) is appropriate given individual patients' variable session time commitment as part of TAU. Payment for study assessments will take place in the form of a check, which can take between 4 to 8 weeks to process. Payment for UP group and TAU session attendance will be in the form of \$5 gift cards to stores that do not sell alcohol or contain a pharmacy (e.g., Dunkin Donuts), which will be provided on an ongoing basis throughout the study.

The following list includes descriptions of each measure being used in the proposed study.

Client Satisfaction Questionnaire ($CSQ-8^{47}$). This 8-item self-report questionnaire will be given to participants in the UP + TAU condition only at the post-treatment assessment to acceptability of and satisfaction with the UP group treatment.

Demographics Questionnaire. This measure assesses age, sex, gender, ethnicity, education, and employment, and will be administered at the screening/baseline visit only.

*Beck Scale for Suicide Ideation (BSI*⁴⁹). This 19-item self-report measure will be used to measure intensity of attitudes, behaviors, and plans to die by suicide over the past week at pre-, mid-, and post-treatment assessments.

Commitment to Sobriety Scale (CSS⁵¹). This 5-item, psychometrically valid self-report measure will be used to assess participants' commitment to sobriety at pre-, mid-, and post-treatment time points.

Craving Scale⁵². This self-report measure, which is made up of three items rated on a visual analogue scale from 0-10 and has been validated for use across multiple substances, will be used to assess craving at pre-, mid-, and post-treatment time points.

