The UP was originally designed as a time-limited, CBT protocol to be delivered in 12 to 16 individual outpatient therapy sessions³⁷. Previous studies have demonstrated that the original UP can be successfully modified for administration in other formats (e.g., 12 2-hour weekly outpatient group sessions⁶⁰, 5 one-hour individual inpatient sessions¹⁹). For this study, the UP will be delivered over the course of 16, 1-hour twice-weekly sessions, delivered over an 8-week period, in order to be consistent with the length of existing group treatment session (1 hour) and average group treatment engagement (8 weeks) at ARMS.

Each of the original 8 UP modules (motivation enhancement, functional assessment of emotions, mindful emotion awareness, cognitive flexibility, countering emotion-driven behaviors, interoceptive exposure, emotion exposure, relapse prevention³⁷) will be delivered to a small group of up to 10 participants. See Table 2 for weekly session content. One UP group will be running at any point in time within ARMS, Admission will be partially rolling, such that new study participants can enter the group intervention at any point through UP Week 5 (and then, for example, would attend UP Weeks 1-4 after UP Week 8). If a participant beginning the group treatment during UP Week 5 misses one of the two UP Week 5 sessions, they will undergo an individual "catch-up" session before UP Week 6 in order to ensure that they have received all the UP Week 5 material before proceeding to UP Week 6. Participants will not be permitted to begin the group during UP Weeks 6-8 as these sessions (interoceptive and emotion exposure exercises) are contingent upon learning the emotion management skills presented during UP Weeks 1-5. Should a group of five participants be randomized to the UP + TAU condition during UP Weeks 6-8, they will wait up to attend their first UP group session until UP Week 1 begins again (up to

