Week 7	Session 14	No	Emotion exposure (UP Module 7):
			-Present the rationale for conducting emotion exposure
	(Repeat		exercises (including the natural course of emotion)
	Session 12)		-Conduct emotion exposure exercise as a group (e.g.,
			imagining an emotional situation, listening to emotion-
			provoking music, or watching an emotional video
			while practicing new emotion management skills)
Week 8	Session 15	No	Relapse prevention (UP Module 8):
			-Review key treatment concepts and emotion
			management skills
			-Identify ongoing opportunities for skills practice
			-Identify long-term goals
Week 8	Session 16	No	Relapse prevention (UP Module 8):
			-Review key treatment concepts and emotion
			management skills
			-Identify ongoing opportunities for skills practice
			-Identify long-term goals
L	1		

VI. BIOSTATISTICAL ANALYSIS

Power: The proposed pilot study is the first, necessary step in obtaining preliminary data to justify future larger, randomized trials. Although we will test for statistical significance, the primary aim is to obtain usable feasibility and acceptability data, as well as to estimate the adjunctive intervention's effect size in order to conduct more adequately powered studies in the future. As such, a formal power analysis was not conducted *a priori*; however, the proposed N (50 subjects) is in line with other recent pilot RCTs examining the feasibility and preliminary efficacy of cognitive-behavioral group interventions for young adults⁶¹ and teens⁶² with SUD.

Preliminary analyses will describe the participants' demographic and clinical characteristics. Comparisons will be made using Mann-Whitney or chi-square tests to determine if the

randomization provided a balanced sample and if participants who dropped out differ from those who did not. All analyses will be conducted using the SPSS and/or Stata statistical packages.

Specific Aim 1: We will use descriptive statistics to report satisfaction ratings with the UP intervention (total CSQ-8 score; *Hypothesis 1a*) and number of UP sessions attended. We will use chi-square tests to evaluate differences in the proportion of participants in each condition who drop out of treatment at the ARMS program during the study period (*Hypothesis 1b*).

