Breach of confidentiality is possible, though highly unlikely because all information will be identified with a numeric code only and stored in a locked file cabinet or on encrypted computerized databases. An enrollment database linking names and study identification numbers will be kept in a secure folder separate from other subject data sources. Only study staff will have access to this database. All staff are or will be fully trained in relevant ethical principles and procedures, including confidentiality. All assessment and treatment procedures will be supervised by the PI. Audiotapes will be erased upon completion of data analysis. We will ask all UP group participants to keep the information that others share during the groups confidential.

Subjects will be informed of all of the aforementioned risks during the consent process.

VIII. POTENTIAL BENEFITS

It is possible that the participants may not receive any direct benefit from participation in the study. However, it is hoped that the experimental intervention could provide relief from substance use related problems, emotional disturbances, and improve the level of functioning exhibited in young adults with SUD and co-occurring emotional distress.

Subjects participating in this study may experience individual benefits from receiving the adjunctive group intervention. The intervention, which will be conducted by a master's or doctoral-level clinician, will be provided to the participants at no charge. Participants will make \$100 for completion of the three assessments and up to an additional \$80 for session attendance. If patients do not complete the full screening visit due to ineligibility, compensation will not be provided as it is anticipated that inclusion/exclusion criteria will be determined within the first 15 minutes of the visit; in addition, every effort will be made to conduct the screening visit immediately following the subject's routine ARMS evaluation feedback or treatment recommendations sessions so that the subject need not travel back to MGH for a separate screening visit. Participants will not be compensated for treatment sessions.

Benefits to future patients, researchers and clinicians could include the development of more effective and efficient treatment for substance use-related problems and emotional distress experienced by young adults.

IX. MONITORING AND QUALITY ASSURANCE

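### Hypothesis 1b's dropout outcome can count UP attendance as retention and its window differs by arm, so the chi-square test cannot separate retention in usual care from attendance at the added group

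*Protocol*

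**What the plan says.** For Hypothesis 1b, Section II (Specific Aims) predicts: "UP participants will be less likely to drop out from treatment at the outpatient program during the study period than those in control condition". Section VI (Biostatistical Analysis, Specific Aim 1) tests it by chi-square on "differences in the proportion of participants in each condition who drop out of treatment at the ARMS program during the study period". It is the only between-arm test under Aim 1; satisfaction and UP sessions attended are reported descriptively.

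Section V (Study Procedures) says that UP + TAU participants receive TAU and will "be offered 16 additional, twice-weekly group UP sessions, also at ARMS". The description of the UP treatment adds: "One UP group will be running at any point in time within ARMS". The outreach rule in the UP + TAU paragraph applies to those who "have two consecutive unplanned absences from a UP group session, up to three attempts to contact will be made regarding their absence". No matching step is given for missed usual-care sessions in either arm.

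The TAU post-treatment assessment falls 8 to 10 weeks after randomization. The UP + TAU one falls within two weeks after each participant's 16th UP session. Groups randomized during UP Weeks 6-8 may wait up to 4 weeks before starting.

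On data, Section V says: "TAU attendance (e.g., number of appointments) for all participants will be tracked by study staff". On payment, it gives $5 per session for "up to 16 UP sessions in the UP+TAU group and up to 16 TAU sessions in the TAU along group".

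**The concern.** The outcome is leaving treatment at a clinic, and the experimental arm is given an extra treatment at that clinic. Nothing in the protocol excludes UP sessions from what counts as ARMS treatment. The one operational dropout rule, in Section V, concerns leaving the study after unanswered contact attempts, not leaving ARMS care. The same behaviour, stopping all usual care, can therefore be scored differently in the two arms.

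Two other features add to this. Only UP absences trigger contact attempts. And follow-up can be longer in the UP arm, which gives its participants more time in which to drop out.

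At stake is what a difference on Hypothesis 1b would mean. Section I (Preliminary Studies) suggests that an emotion-focused treatment may be associated with less dropout. Lower recorded dropout could reflect that, or only that 16 further appointments at the same clinic were offered and absences from them followed up. One test on one combined outcome cannot tell these apart.

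**Working it through.** The protocol states no dropout rate, effect size or power for Hypothesis 1b, so there is no figure to reproduce. The check has three parts.

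**1. How the wording scores the same behaviour**

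| Behaviour | UP + TAU | TAU |
|---|---|---|
| Stays in usual care | Retained | Retained |
| Leaves usual care, attends UP at ARMS | Retained, on the plain wording | Not possible |
| Leaves all ARMS sessions | Dropped out | Dropped out |

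**2. Size of the counting effect**

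Let p be the true proportion leaving usual care, equal in both arms, and q the share of UP-arm leavers who still attend UP. Both are assumptions.

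Recorded dropout is p in TAU and p(1 − q) in UP + TAU. The gap with no true difference is p − p(1 − q) = pq.

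| p | q = 25%: UP arm recorded | Gap | q = 50%: UP arm recorded | Gap |
|---|---|---|---|---|
| 20% | 15% | 5 points | 10% | 10 points |
| 30% | 22.5% | 7.5 points | 15% | 15 points |
| 40% | 30% | 10 points | 20% | 20 points |

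To see what this does to the test, the Pearson chi-square rejection probability was obtained by exact binomial enumeration. A two-sided 5% level is assumed, because the protocol states none, and participants are treated as independent. A 2:1 split of N = 50 is about 33:17. Randomization in groups of five gives ten groups, so whole groups give 35:15 or 30:20. The probability of a significant result favouring UP, with equal true usual-care dropout, is:

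| Split | p | q = 0 | q = 25% | q = 50% |
|---|---|---|---|---|
| 33:17 | 30% | 2.7% | 8.9% | 23.8% |
| 33:17 | 40% | 2.5% | 11.0% | 33.4% |
| 35:15 | 30% | 2.7% | 9.2% | 25.7% |
| 35:15 | 40% | 2.5% | 10.4% | 32.5% |
| 30:20 | 30% | 2.4% | 8.4% | 24.1% |
| 30:20 | 40% | 2.7% | 10.8% | 32.8% |

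At q = 0, where UP attendance does not rescue anyone from being counted, the rate is about the nominal 2.5% in that direction. These figures cover counting only, not outreach, payment or the window.

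**3. The window**

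TAU: 8 to 10 weeks from randomization. UP + TAU: a wait of up to 4 weeks, 8 weeks of twice-weekly sessions, and up to 2 weeks to the assessment, so up to 4 + 8 + 2 = 14 weeks. A further wait is possible if there are too few participants to form a group; no limit is stated for it. If dropout accrues with time, the longer window raises it in the UP arm, the opposite direction to part 2.

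**The case against.** The strongest reply is that the protocol nowhere says a UP-only attender counts as retained. It treats UP as additional to TAU and tracks TAU attendance separately, and an analysis plan that is not shown could define dropout on usual care. That stands as a limit: the point rests on the plain wording of the hypothesis and of the analysis, not on an explicit counting rule.

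Second, whole-program retention is a legitimate outcome for an add-on trial. Someone attending twice-weekly therapy at ARMS is in treatment there. A usual-care-only count has its own flaw: TAU has no required dose and some patients use one modality only, so a participant who swaps a usual group for UP could be scored a dropout. This stands too, and it is why both outcomes are needed and neither should replace the other.

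Third, the contact rule in Section V speaks of a 10-week study, which may be the intended common period. If so, the protocol should say so for Hypothesis 1b, because the UP schedule can run past it.

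A reader might infer that payment tilts the result towards UP. The documents do not support that: rate and cap are the same in both arms, and only the type of paid session differs. On a usual-care outcome, payment would if anything favour TAU, the only arm paid for usual care. Paying for any ARMS session under the same cap would not settle it, since 16 UP sessions at $5 already use the full $80.

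**Conclusion.** The point holds as a problem of interpretation. On its plain wording the Hypothesis 1b outcome can include attendance at the intervention, outreach is specified for one arm only, and the window differs by arm. The single test therefore cannot separate retention in usual care from attendance at the added group.

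A reader might go further and conclude that the comparison is biased in favour of UP. The documents do not support that. Counting and outreach favour UP, the longer window may work against it, and the net direction is uncertain. The 5 to 20 points are not an estimate of expected bias either. They are the product of two assumed ranges (usual-care dropout of 20-40%, with 25-50% of leavers still attending UP) and apply only if UP attendance is counted as retention.

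This is a pilot with no power calculation, and no sample-size figure is affected. What changes is the claim that Hypothesis 1b can support.

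**What to change.** 1. Measure dropout in both arms over the same fixed window from randomization.
2. Use the attendance tracked for all participants to analyse dropout from usual-care (non-UP) ARMS services by arm. Report whole-program dropout beside it, labelled as including UP sessions.
3. Base any claim that UP improves retention in usual care on the usual-care analysis. Note that UP may replace a usual group, and that UP-only outreach and arm-specific paid sessions remain as limitations. Payment need not be redesigned.
4. Separately, reconcile Section VIII (Potential Benefits), "Participants will not be compensated for treatment sessions", with the session payment of up to $80 in Section V, the compensation for up to two weekly treatment sessions in Section VII (Risks and Discomforts), and the $80 given in Section VIII itself. This does not bear on the Hypothesis 1b outcome.

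The cost is one more analysis from data already to be collected, and a result that may look less favourable to UP.
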